3.2. Appointment Not Found

Check if the appointment is not listed above.

4. Investigator-Initiated Study

* Is this an investigator-initiated study?

Yes No

Study Team

1. Points of Contact Selection

Points of contact can edit the application and will receive email notifications about this submission.

Please do not use personal email addresses (e.g., Gmail, Hotmail, etc.). A campus business email can be changed following the instructions [here](#).

If the PI is serving as the only study point of contact, indicate that [here](#).

Can't find someone in the chooser? See [this FAQ](#) for help.

To register a NetID, [click here](#).

1.1. Funding Sources

For **federal funds**, pending sources may be listed if the grant has received a highly meritorious score. For example, an impact score of <30 is an indication of a highly meritorious NIH grant proposal. Receipt of a request for Just In Time (JIT) documentation is another indication of a highly meritorious proposal.

For **non-federal funds**, pending sources may be listed if you have confirmation from the sponsor that funding will be awarded due to merit AND the sponsor has a peer-review process.

For **industry**, do not select industry sponsors who are only providing drug/device OR only limited support for the study.

* Use this chooser to select each funding source administered through UW-Madison that will support this study or project.

Funding Source Details

View	PI Name	[name]
	Proposal ID	MSN242995
	Award ID	MSN242995
	Funding Title	ADRD Prevention Messaging to Increase Smoking Cessation Attempts in Older Adult Smokers
	Project ID	No Value Entered
	Sponsor (Source)	DHHS, PHS, NATIONAL INSTITUTES OF HEALTH
	Sponsor Reference Number	1K23AG067929-01A1
	Primary Sponsor	No Value Entered

Funding Source Details

Primary Sponsor Reference Number	No Value Entered
Federal	Yes
Status	Active
Start Date	5/1/2021
End Date	2/28/2026

2. Other Funding

* Do you have pending or approved funding NOT listed on this page?

Yes **No**

Conflict Of Interest

Please review the study team member Outside Activities Report (OAR) and managed entities data below before answering the questions on this page.

The following study team members have not completed their OAR for the year:

[name], [name], [name], [name], [name]

NOTE: Per campus policy all study team members must submit an OAR every year and keep it up to date.

No study team members have any managed entities at this time.

1. Intellectual Property

* Do any study team members involved in the design or conduct of the research (including their spouses and dependent children) own intellectual property that will be used in the study or project?

Yes No

2. Other Entities

* Besides the sponsor(s) of this project or entities listed above, do any study team members have a fiduciary or financial relationship with entities that will be involved in this study or that may be significantly affected by it?

Yes No

3. Incentives

* Do any of the study team receive any incentives for recruiting human subjects or any other purpose directly related to the study or project?

Yes **No**

VA Status

All studies that fall under Madison VA purview must be reviewed and approved by the VA Research and Development (R&D) Committee in addition to being reviewed by the Health Sciences IRB. For information about the VA R&D Committee review process, please contact

[contact].

1. VA Status

* Does this study involve the Madison VA (Wm. S. Middleton VA Hospital); e.g., funding from the VA, conducted under VA appointment, use of VA facility, recruitment of veterans or use of their data or samples at the Madison VA?

Yes No

Scientific Review: PRMC & CRU

1. Cancer Related

* Is the scientific question of the protocol cancer related?

Yes No

2. Targeting Cancer Patients

* Are you specifically targeting cancer patients for enrollment in this study?

Yes No

3. Use of Cancer Data or Images

* Does this study involve the review and/or use of biological specimens/data/images/records from cancer patients?

Yes No

4. Use of CRU

If the answer to this question is Yes, you must upload a copy of the CRU application to the Submit activity form.

* Will this study use the Clinical Research Unit (CRU)?

Yes No

UROC Determination

Submission of research studies that meet certain criteria must be reviewed by either Protocol Review and Monitoring Committee (PRMC) or UW Health/SMPH Research Operations Committee (UROC) prior to review by the IRB. The UROC Endorsement Letter, if review is required, must be uploaded prior to submission of your protocol to the IRB. For more information about UROC review, visit the [**UROC KB Page**](#).

1. Criteria for UROC Review

* Select all the criteria below that apply to your study.

None of the above apply or the study was approved by the IRB prior to July 1, 2024.

ClinicalTrials.gov Information

This page is designed to aid in identifying ClinicalTrials.gov registration requirements. Registration may be required by the FDA, NIH, or if you are planning to publish in a journal that follows International Committee of Medical Journal Editors (ICMJE) guidance. Please answer each question carefully.

UW-Madison has a free service available to assist you in registering your record with ClinicalTrials.gov. Contact [contact] for more information.

For information on registration and results reporting requirements see our [KnowledgeBase page](#) or contact the Office of Research Compliance at [contact].

1. Study Intervention(s)

Prospective assignment means enrolling study subjects and collecting data on them in the future. It is a study not solely reliant on existing or retrospective data. It is not a requirement to have multiple groups or arms for a study to be considered prospectively assigned.

An **intervention** is any manipulation of the subject or subject's environment for the purpose of modifying one or more health-related biomedical or behavioral processes and/or endpoints. Any study that is not observational (where participants may receive a drug, device, medical procedure, or behavioral intervention as part of their standard clinical care) should be considered interventional. Examples include: drugs/small molecules/compounds; biologics; devices; procedures (e.g., surgical techniques); delivery systems (e.g., telemedicine, face-to-face interviews); strategies to change health-related behavior (e.g., diet, cognitive therapy, exercise, development of new habits); treatment strategies; prevention strategies; and, diagnostic strategies.

A **health-related biomedical or behavioral outcome** is defined as the pre-specified goal(s) or condition(s) that reflect the effect of one or more interventions on human subjects' biomedical status, behavioral status, or quality of life. Examples include: positive or negative changes to physiological or biological parameters (e.g., improvement of lung capacity, gene expression); positive or negative changes to psychological or neurodevelopmental parameters (e.g., mood management intervention for smokers; reading comprehension and /or information retention); positive or negative changes to disease processes; positive or negative changes to health-related behaviors; and, positive or negative changes to quality of life.

* Are subjects prospectively assigned by the protocol to any intervention(s) that are being evaluated for any health-related

biomedical or behavioral outcomes?

Yes No

2. ClinicalTrials.gov Determinants

* Check the box(es) that apply to this study:

NIH funded, when registration is a required condition of the grant (consult your award letter or with your NIH Program Officer if unsure)

3. FDA or NIH Requirement

* Based on your responses, registration with ClinicalTrials.gov may be required by the FDA or NIH. Will UW-Madison (study team or service line support staff) register the study with ClinicalTrials.gov?

Yes No

External Collaborations

1. Outside UW Activities

* Will any UW/UW Health or Madison VA personnel conduct any of the following study activities at locations outside the UW/UW Health or Madison VA: subject recruitment, obtaining informed consent, or interacting or intervening with subjects?

Yes No

2. Requesting UW Serve as IRB

Please note that you must consult with RELIANT before you submit a request for the UW to serve as the reviewing IRB for external sites or individuals. A consultation may be requested here.

* Are you requesting that UW Madison serve as the reviewing IRB for any external sites or individuals?

Yes No

Sharing Data Outside UW

1. Sharing Data Outside UW Madison

* Will subject data, images, or specimens be shared outside the UW Madison?

Yes No

Study Procedures and Special Populations

1. Study Procedures Involved

Select "Review or use of information from health care records"

* If your study involves any of the following special procedures or considerations, additional information may be needed. Select all that apply. If none apply, check Not Applicable.

Creation of audio or video recordings or photographs

Interviews, focus groups, surveys, questionnaires, assessments (e.g., QOL, SCID, BDI, etc.)

2. Special Populations

If you will collect data points identifying individuals as any of the following, select the corresponding box(es).

* Is the research designed to include any of the following populations? Select "Not Applicable" if the research will not include any of the populations below. NOTE: If enrolling pregnant women, children, or prisoners, and you can identify them as such, check the box.

Poor/uninsured, elderly/aged, or educationally disadvantaged

Research Design and Procedures

1. Overall Purpose

Describe the research questions or gap in knowledge the study proposes to address or contribute to in language that someone who is educated but not an expert in the field can understand.

- * What is the overall purpose and aim of this project or study?

The purpose of this research is to evaluate messages that motivate older smokers to make quit attempts using evidence based smoking treatments (EBSTs).

2. Pre-Existing Information/Background Knowledge

- * What prior information or knowledge exists to support the conduct of this project or study?

An estimated 5.8 million people have Alzheimer's disease and related dementias (ADRD) in the U.S., costing \$290 billion per year. The incidence of ADRD is expected to triple by 2050, costing an estimated \$1.1 trillion per year. Due to the rapid growth and tremendous impact of this disease, focus has shifted towards targeting modifiable risk factors to prevent and slow the development of ADRD, potentially preventing approximately 40% of ADRD cases. A candidate risk factor, cigarette smoking, is the leading preventable cause of death and disability in the U.S., resulting in 480,000 deaths and costing over \$300 billion each year.

Epidemiological studies show that cigarette smoking is prospectively associated with a 70% increased risk of Alzheimer's disease (AD) dementia onset, accounting for at least 13.9% of ADRD cases. Smoking directly increases the likelihood and severity of at least five risk factors for ADRD onset (i.e., diabetes, hypertension, stroke, heart disease, and high cholesterol). Smoking cessation can lower these risk factors, even among an aging population.

Regardless of genetic risk, healthy lifestyle modifications such as smoking cessation can cut the risk of ADRD in half. Due to the known relations between smoking, other ADRD risk factors, and ADRD, the World Health Organization, Institute of Medicine, and Alzheimer's Association state that smoking cessation is among the top priorities for reducing cognitive decline and preventing onset of dementia.

Fortunately, evidence-based smoking treatments (EBSTs) exist that can double or triple cessation success. Older adult smokers are at especially high risk for ADRD. Currently, there are 19 million smokers ages 45 and older. Given the predicted doubling of older adults in the next 25 years, helping older smokers quit is a vital public health priority. Unfortunately, older smokers are half as likely to attempt to quit smoking compared to younger adults. Lower cessation efforts in older smokers may be a function of both clinician inaction and dysfunctional beliefs/motivational deficits of older smokers. Compared to younger adults, older smokers are less likely to receive advice to quit or be offered EBSTs (e.g., pharmacotherapy, counseling) by healthcare professionals. Moreover, older smokers' doubts about the benefits of quitting later in life and the efficacy of smoking cessation interventions may reduce older smokers' motivation to quit.¹³ Importantly, older smokers who do attempt to quit are more likely to maintain abstinence than younger smokers when using EBSTs. The chief obstacle to reducing smoking among older adults does not appear to be treatment efficacy, but rather failing to motivate this underserved population to make quit attempts using EBSTs.

According to the Health Belief Model, impactful motivational messages for older smokers should focus on threats they perceive as important and personally relevant and messages should be offered with a feasible, effective course of action to address the health threat. Older adults' greatest aging-related fear is cognitive decline and developing dementia; it is both important and relevant. The link between smoking and ADRD risk factors and the availability of EBSTs offers an effective strategy to respond to this threat. Unfortunately, the indirect relation between smoking and ADRD risk expressed via known ADRD risk factors has not been clearly articulated to the general or medical community, and is not used as a motivator for smoking cessation. Building novel interventions for translation will facilitate more rapid dissemination and subsequent impact on public health. The overarching objective of this proposal is to test a readily translatable Stage 1 motivational intervention for smoking cessation in older adults consisting of: (1) a novel patient-informed motivational message promoting smoking cessation; and (2) ready access to EBSTs for smoking cessation. This responds to two of NIA's goals: (1) develop effective interventions to maintain health, well-being, and function and prevent age-related diseases/disabilities; and (2) disseminate information to the public, medical, and scientific communities. This project will evaluate the motivational impact of a message packages developed from a previous study (IRB# 2020-1429).

3. Study Procedures and Interventions

Provide an overview of the types of records that will be reviewed, what information from these records will be collected, and the kinds of analyses that will be performed on the study data. If data from multiple sources will be used describe this here (e.g., medical record information connected to imaging or billing information or data from multiple institutions collated).

* Briefly describe the procedures and interventions that will be performed for this project or study and all study arms involved. Do not include information on recruitment or consent.

Participants will be randomized to one of four messaging interventions; 1) active control (CDC TIPS from former smokers campaign), 2) active control (American Lung Association campaign), 3) treatment condition including message package focused on the link between smoking and dementia, 4) no intervention control. The messaging intervention will be delivered via mail, which will include a QR code link that will allow participants to view associated motivational video. Participants will then complete the first of 2 telephone survey assessments (lasting ~30 minutes). Participants will then receive three mailers over the next couple of months and will schedule their follow-up call approximately 2.5 months later. At one to two weeks, one month, and two months after this call they will be mailed the corresponding message to their group (no intervention group will not be sent a message package). Follow up telephone assessments will occur within approximately 1-2 weeks following intervention exposure marked by date the intervention mailer was sent.

Up to 20 participants randomized to the intervention condition will complete an additional brief qualitative interview following their second telephone survey assessment (lasting ~20 minutes). The qualitative interview will focus on the perceived impact of the message, preferred number of message exposures, preferred modality of message receipt, and suggested improvement to message content. Health Believe Model (HBM) constructs assessed include: perceived severity, perceived benefits (i.e., efficacy of EBSTs; impact of quitting on ADRD risk), perceived barriers (i.e., knowledge of how to access EBSTs in healthcare setting), and self-efficacy (i.e., confidence in ability to quit in the next 30 days).

4.

Incidental or Adventitious Findings

* Will any study procedures produce incidental or adventitious findings (e.g., imaging scans, laboratory blood tests, depression screening questionnaires, etc.)?

Yes **No**

5. Instruments/Technology Involved (Includes AI/ML Algorithms)

This question is intended to identify projects involving the development or use of medical devices. This does not apply to surveys, questionnaires, or statistical analysis software.

* Are there instruments or technology of any kind, including software, tests run on samples, and algorithms, used or developed in the study?

Yes **No**

Subject Identification: Medical Records

1. Medical Record Use

* Will medical records be used to identify subjects or records?

Yes **No**

Risks and Benefits

1. Direct Benefits Intended

For this type of research there are generally no direct benefits to subjects. The response to this question, "There are no direct benefits to subjects", would be acceptable.

* Are any of the research activities intended to directly benefit subjects?

Yes No

2. Potential Benefits to Society

Describe how the research might help future patients.

* Describe the importance of the knowledge reasonably to be gained from this study and what benefit the research may provide to society.

The knowledge gained from this study will identify the most impactful motivational message to promote smoking cessation and the use of evidence-based cessation treatment in older adult smokers. This population of smokers are particularly at risk for all of the known health effects of smoking, including dementia.

3. Direct Physical Intervention

A physical intervention refers to study procedures that may pose a risk (however minimal) to a subject's body (e.g., blood draws, MRI scans, drug or device trials, exercise, dietary restrictions/supplements). Examples of activities that are NOT physical intervention include obtaining informed consent and administering surveys.

* Does this study involve direct physical intervention with subjects?

Yes No

4. Potential Psychosocial Risks

For this type of research the risks to subjects are generally limited to the risk of breach of confidentiality. The response to this question, "There is a risk of breach of confidentiality", would be acceptable.

* Describe any potential psychosocial risks to subjects, such as psychological stress or confidentiality risks (including risk to reputation,

economic risks, and legal risks).

There is a risk of a confidentiality breach.

Participants may become upset or experience discomfort.

5. Procedures to Minimize Risks

The response to this question should address how the risk of breach of confidentiality will be minimized. For example, it could be described that the study team has several measures in place to protect against a breach of confidentiality, such as limiting the number of people who view identifiable information, coding study instruments, storing study data in restricted areas and on computers that are password-protected, only transmitting coded data outside the institution (if data will be shared), and using a secure web-interface to transmit data off-site (if data will be shared).

* Describe the procedures in place to minimize risks from all interventions performed for research purposes. This should include activities in place to identify, monitor, mitigate, and eliminate risks to the degree possible.

Data will be stored securely according to campus policy.

Participants will be informed of the approximate length of study activities during the consent process and will be offered the opportunity to take breaks during the study activities if needed.

Participants will be informed about all aspects of the study during consent and have the option to skip or withdraw from any activities that make them upset or uncomfortable.

Subject Population

1. Total Subjects

You must provide an integer. If you are enrolling a range of subjects (e.g., 50 to 100 subjects), enter the larger number.

* Provide the number of subjects that will be enrolled at sites for which UW Madison is serving as the reviewing IRB.

220

2. Inclusion Criteria

* Describe the main inclusion criteria.

- Adults between the ages of 50-80
- Self-reported current smoker
- Do not hold a current diagnosis of dementia or Mild Cognitive Impairment (MCI)
- Can read/write in English

3. Exclusion Criteria

* Describe the main exclusion criteria.

History of Mild Cognitive Impairment (MCI) or dementia.

4. Targeted Populations

Populations could be racial/ethnic, sex, or gender (this also applies to gender identity, or lack thereof).

* Will this study target or exclude specific populations?

Yes No

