4.1. Transcriber Details

* Indicate who will perform the transcription.

Transcription will be done by a professional transcription service.

Interviews, Focus Groups, Surveys, Questionnaires

1. Tool Details

* Describe the interview tools, questionnaires, or surveys that will be used. Click the add button to provide information about each tool to be used.

View	Tool Description	Optional Qualitative Interview
	Tool Standardized	No
	File name	Outline of Qualitative Interviews_V1_2023.10.13.docx
	Tool Manner	Telephone
	Tool Manner Other	No Value Entered
	Date Modified	10/20/2023

View	Tool Description	Follow Up Survey
	Tool Standardized	No
	File name	MCAS Aim 3 3 Month Follow Up Questionnaire_V2_10_20_23_trackedchanges.docx
	Tool Manner	Telephone
	Tool Manner Other	No Value Entered
	Date Modified	10/20/2023

View	Tool Description	Baseline Survey
	Tool Standardized	No
	File name	MCAS Aim 3 Baseline Questionnaire_V5
	Tool Manner	Telephone

Tool Manner Other	No Value Entered
Date Modified	9/13/2023

2. Cognitive or Psychological Assessment

* Are any of the uploaded instruments used to assess cognitive or psychological status or function?

Yes **No**

Interviews, Focus Groups, Surveys, Questionnaires Cont.

1. Focus Group

* Will the study involve conducting focus groups?

Yes **No**

2. In-Home Visit

* Does the study involve in-home visits?

Yes **No**

Supplemental Information

1. Additional Documents

Provide any additional relevant documents (e.g., data sharing agreements, letters of support, MOUs, site permission letters), if applicable.

-  active control flyer 1(0.01)
-  active control flyer 2(0.01)
-  active control flyer 3(0.01)
-  active control videos(0.01)
-  fear flyer(0.01)
-  fear video(0.01)
-  MCAS Mailing 1 Cover Letter Active Control and Treatment Condition (Groups 1, 2, 4)_v2(0.02)
-  MCAS Mailing 1 Cover Letter No Treatment Condition (Group 3)_v2(0.02)
-  MCAS Mailing 2 Cover Letter Active Control and Treatment Condition (Groups 1, 2, 4)_v2(0.02)
-  MCAS Mailing 3 Cover Letter Active Control and Treatment Condition (Groups 1, 2, 4)_v2(0.02)
-  MCAS Mailing for Follow-up Payment v1_11_8_23.docx(0.01)
-  MCAS Video Group 1 Email 1.docx(0.01)
-  MCAS Video Group 1 Email 2.docx(0.01)
-  MCAS Video Group 1 Email 3.docx(0.01)
-  MCAS Video Group 1 Email 3_V2_10_20_23_trackedchanges.docx(0.01)
-  MCAS Video Group 2 Email 1.docx(0.01)
-  MCAS Video Group 2 Email 2.docx(0.01)
-  MCAS Video Group 2 Email 3.docx(0.01)

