-  MCAS Video Group 2 Email 3_V2_10_20_23_trackedchanges.docx(0.01)
-  MCAS Video Group 4 Email 1.docx(0.01)

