1.1. Describe Documents

Describe what additional documents were added in 1.

We have added a cover letter to be included with the participants' final study payment.

Final Page

1. Assurance

- The information presented in this application is accurate;
- If the application is being submitted on behalf of the Principal Investigator (PI) rather than by the PI, the information presented was done so with the PI's agreement; and
- The specific aims and description of research (including subject population, subject interventions, collaborators, performance sites, and general scope of work) in this IRB application are consistent with those described in the sources of support listed as providing financial and/or material resources to conduct this study.

* Do you certify the above statements?

Yes No

2. Complete and Submit Application Instructions

To complete and submit this application to the IRB office, please follow the steps below:

- Select 'Finish' or 'Exit' on this page to be directed to the application workspace.
- In the application workspace, click the Submit activity to send the application to the IRB office. NOTE: The Submit activity is only available to certain study team members.

Statistical Analysis Plan

[name] will use SPSS to examine differences in changes in motivation (primary), number of 24 hour quit attempts (secondary), and use of evidence-based treatment (secondary) between groups. Specifically, she will examine differences in mean scores from baseline and follow up between the treatment group and three control groups. Given the pilot nature of this study, we will not be statistically powered to conduct regression analyses. Therefore, descriptive analyses will be the primary analytic method.

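### Could the differing arm numbers in the procedures section and on the study materials swap treatment with no intervention?

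*Combined protocol and SAP*

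**What the plan says.** Three places in the combined protocol and SAP bear on this.

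- **Research Design and Procedures, item 3 (Study Procedures and Interventions).** One sentence lists the four conditions. Two active controls come first and second, followed by "3) treatment condition including message package focused on the link between smoking and dementia, 4) no intervention control". The same answer adds in brackets that the "no intervention group will not be sent a message package".
- **Supplemental Information, item 1 (Additional Documents).** The uploaded files carry group numbers. One letter is titled "MCAS Mailing 1 Cover Letter No Treatment Condition (Group 3)_v2(0.02". The letters for the other conditions run from "MCAS Mailing 1 Cover Letter Active Control and Treatment Condition (Groups 1, 2, 4)_v2(0.02" to "MCAS Mailing 3 Cover Letter Active Control and Treatment Condition (Groups 1, 2, 4)_v2(0.02". Video emails are listed for Groups 1 and 2, and the list ends with "MCAS Video Group 4 Email 1.docx(0.01". Flyers and videos are named by content, for example "fear flyer(0.01", without a group number.
- **Statistical Analysis Plan.** No codes are used. The analyst is named by role in the sentence that "she will examine differences in mean scores from baseline and follow up between the treatment group and three control groups".

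**The concern.** Read as codes, the two numberings disagree on two of the four arms. Number 3 is the dementia-message treatment in the procedures list and the no-treatment group on the materials. Number 4 is no intervention in the list and a message-receiving group on the materials. Nothing in the supplied text maps one onto the other.

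The analysis is a descriptive comparison of group means in SPSS, so correct arm labels matter. If the data set holds a group variable from 1 to 4 in the materials' numbering, and its value labels are taken from the procedures list, the two arms of greatest interest are exchanged. The treatment versus no-intervention difference changes sign, and the no-intervention arm stands in for treatment in both comparisons with active controls. In a small pilot, a reversed difference might not look implausible enough to prompt a check.

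**Working it through.** The plan gives no figure to reproduce, so the check sets the texts side by side and then asks what would have to happen for the labels to be exchanged.

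**1. The two numberings**

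| Number | Procedures list | Titles of study materials |
|---|---|---|
| 1 | active control (CDC campaign) | message group |
| 2 | active control (American Lung Association campaign) | message group |
| 3 | dementia-message treatment | no treatment |
| 4 | no intervention | message group |

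Numbers 1 and 2 are compatible; 3 and 4 are not. If Groups 1 and 2 are the two active controls, Group 4 is the treatment arm by elimination. No title says so.

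**2. Are both columns codes?** The procedures section numbers the items of a sentence and does not call any arm Group 3 or Arm 4. After the list it refers to arms by role: the group without intervention, and the intervention condition. The background section of the same form numbers ordinary items in sentences in much the same way (the two parts of the intervention, the two institute goals). The word Group followed by a number occurs only in the file titles.

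**3. Are the file titles consistent?** Yes. All four cover-letter titles give the same split. The no-treatment group has one letter, at the first mailing, while the other three groups have letters at all three mailings. Video emails appear for Groups 1, 2 and 4 and none for Group 3. This agrees with the procedures text, under which the no-intervention arm gets no message package. The title of the Group 3 letter states number and condition together, so for that arm it serves as a key.

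**4. What would an exchange do?** Write means relative to no intervention: treatment d, active control a, no intervention 0.

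- Correct labels: treatment minus no intervention = d - 0 = d; treatment minus active control = d - a.
- Treatment and no intervention exchanged: 0 - d = -d, a shift of -d - d = -2d; and 0 - a = -a, a shift of -a - (d - a) = -d.
- Participants affected: with the enrolment ceiling of 220 and equal allocation assumed, 220/4 = 55 per arm and 2 × 55 = 110.
- One key used throughout: shift 0.

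The documents give no expected effect, so d has no value here. Putting the shift in standard deviations would only restate twice an assumed effect.

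**5. What would it take?** All of the following would have to hold: the data set carries bare numbers; the analyst does not use the codes under which participants were randomised and mailed; the analyst labels the values from the order of a sentence in the ethics application; and nothing later exposes the error. The last condition is hard to meet. Up to 20 participants from the intervention condition are to be interviewed about the message after the second survey, so staff must identify that arm correctly during the study. Someone who had been sent no message could hardly answer those questions.

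**The case for a change.** The best case for acting is that the procedures section is the only supplied text that defines the arms, and it answers a form question asking for all of them. The study plainly does use group numbers, so someone looking for their meaning would naturally turn there and get two of four wrong. A slip in a single file title cannot explain the mismatch, because several titles agree. The titles also pool Groups 1, 2 and 4, and the video emails carry only a number. From the supplied text, the treatment arm's code can therefore be inferred but not read. The analysis plan gives no codes and describes no check of assigned arm against what was mailed. Relabelling would cost almost nothing.

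Most of this is accurate. The digits do differ, and the supplied text contains no full key. It does not follow that the plan lacks one: the randomisation list, the contents of the letters and emails, and any data dictionary are not in the supplied text. Nor does it show that a mailing or a label was wrong. Low cost makes tidying the labels reasonable housekeeping, but it does not turn a difference in listing order into a fault in design or analysis.

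**Conclusion.** This is a clerical slip and calls for no change to the plan. The order in which the procedures section lists the arms differs from the group numbers in the file titles for two of four arms. Arms, endpoints, contrasts and procedures are the same under either numbering. The comparison in the Statistical Analysis Plan is stated by role, and an analyst carries it out with the codes used to assign and mail participants. On that footing the effect on every contrast is zero.

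The conclusion rests on two readings: that the digits in the procedures section mark list items, as their use there suggests, and that the study has a working allocation key, as any trial mailing different packages by group must. The second cannot be confirmed from the supplied text. If both failed and the labels were exchanged, the treatment versus no-intervention difference would reverse sign. That is a hypothetical handling error, and the documents offer no evidence of it.
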